We believe that the difference between groups will be large (50% or greater) given that LNG ECx1 in obese women appears to be equivalent to placebo (normal ovulation) as well as the large PK differences we found in our preliminary studies. However, we have chosen a more conservative difference (30%) in which to base our sample size calculations to ensure we have the ability to capture a range of differences. A sample size of 62 will achieve 80% power to detect a 30% difference in the proportion of cycles that demonstrate inhibition of follicular rupture (yes/no) using a two-sided Z test with a 5% significant level assuming 90% rate of normal time to ovulation in LNG ECx1 dose group. **We plan to screen up to 80 women to account for screen failures and enroll a total of 70 women to account for drop out.**

Part 2 UPA-EC, obese BMI and a weight of 176 lbs or more and normal BMI and a weight of less than 176 lbs, randomized cross-over trial.

Specific Aim: To compare the pharmacokinetic parameters and pharmacodynamic profile of emergency contraception containing ulipristal acetate between obese and normal BMI women, and to determine if dose escalation improves how well it works in obese women.

Hypothesis: The peak drug level of UPA-EC is lower in obese women than in normal BMI women which adversely impacts the therapeutic effect and dose escalation will improve drug efficacy for obese women.

[figure not shown]

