(TUS). The TUS will be performed using a high-resolution transvaginal ultrasonography (GE Ultrasound OR, 9900 Innovation, Voluson eBT11) to monitor follicular development and evidence of ovulation. During the treatment cycles, study medication will be dosed on the day a 15 mm follicle is visualized. Both the normal and obese BMI groups will undergo treatment cycle 1 and receive a standard dose of UPA EC (30mg) or ECx1. After at least one washout cycle, only the obese group will complete treatment cycle 2 and receive a double dose of UPA EC (60mg). Study medications will be given by study staff and ingestion will be directly observed. Prior to ingesting study medication in each treatment cycle, women will undergo urine pregnancy testing. Study end will be at the onset of menses at the end of the treatment cycle (defined as two consecutive days of spotting/bleeding). We estimate that approximately up to 12 visits in the treatment cycles depending if delay in ovulation occurs.

During each treatment cycle, PK parameters will be obtained via serum samples through an indwelling catheter. IV placement in obese women can be challenging. We will enlist the assistance of OHSU's NIH funded CTSA nursing staff or IV therapy, if necessary, to place IVs in our obese cohort in order to ensure the least traumatic process for our subjects. We plan to obtain samples at 0.5, 1, 1.5, 2, 3, 4, 24, 48, 72, 96, and 120 hours for our normal controls in treatment cycle 1 and a subset of the obese cohort (n=30) in both treatment cycle 1 and 2. The IV will be left in place for the closely spaced samples and then single samples via phlebotomy will be obtained on the samples timed at 24 hours and later. This extended sampling scheme will allow us to determine a more accurate area under the curve by having observed rather than estimated values. Furthermore a prolonged sampling scheme will enable estimation of additional PK parameters that can lead to mechanistic insights.

Of note, Eastern Virginia Medical School will not be recruiting or enrolling participants for the Part 2 – UPA Normal BMI cohort as enrollment of the 12 participants for this group is complete.

Procedure flow for obese BMI study groups

	Screening Visit (1 visit)	Treatment Cycle 1 Starting Cycle day 6-8 (up to 12 visits)	Washout Cycle 2 (no visits)	Treatment Cycle 3 Starting Cycle day 6-8 (up to 12 visits)
Consent, Screening tests and medical history	X			
Phone or email contact			X	
Blood draws	X	X		X

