Data Analysis & Sample Size: To ensure equality between treatment arms at baseline, we will compare participant demographics using t-test or chi-square test and descriptive statistics, such as mean, median and percentages within each group will be reported. The primary outcome analysis will compare the proportion of women with a delay in follicular rupture of at least 6 days (yes/no) between obese women taking UPA ECx1 versus ECx2 using McNemar's test. Only the women who have completed the two treatment cycles will be included in this portion of the analysis. Although we expect absence or ignorable "period" effect, we will further describe the difference between ECx1 and ECx2 with odds ratios using the generalized estimation equation adjusted for period and any other confounders using all available data. We will check the accuracy of our findings against a normal BMI control group using standard dosing, ECx1 using chi-square test. Follicle rupture will be defined as the disappearance of or >50% reduction of size of the leading follicle. Confirmation of ovulation will be supported by LH, P4, and E2 levels. Descriptive statistics will be utilized to report LH and P levels [mean (standard deviation)], follicular diameter [median (range)], and cycle day [median (range)] on the day of EC ingestion during the treatment cycle. Additionally, inhibition of follicular rupture will be plotted by LH status (no surge, start of LH surge, or after LH peak) [2,17] for each cycle as well as mean LH, P4, and E2 levels over time and the time of treatment to follicular rupture.

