A sample size of 73 will achieve 80% power to detect a 20% difference in the proportion of cycles that demonstrate at a delay in follicular rupture (yes/no) using a two-sided McNemar test with a Bonferroni-adjusted 2.5% significant level. We estimate that 40 women will choose to participate in Aim 2 after completing Aim 1 studies and plan to screen an additional 58 women to account for screen failures for a total enrollment of 80 women to account for drop out. We believe that the difference between groups will likely be smaller given the clinical information (50% or less). We have chosen a difference of 20% in which to base our sample size calculations. We have consciously chosen not to enroll an adequately sized normal BMI group to detect the same amount of difference (20%) given that there are published PK/PD standards. We are utilizing this group to verify the accuracy of our findings under our environment, the targeted 10 total number of subjects (after 12 screening) in the control arm would achieve the 80% power to detect 47% difference in follicular rupture given the 73 of women taking UPA ECx1 using two-sided Z test with 2.5% significance level. The total number of subjects in the control arm was chosen as a convenience sample but this number of subjects should supply us with an adequate amount of data to ensure that our PK/PD results are similar to published values in a normal BMI cohort.

Protection of human subjects:

1. Risks to Subjects

Human Subjects Involvement and Characteristics

Reproductive-aged (18-35 year old), ovulatory, healthy women with a normal or obese BMI with no contraindications to the study medications and not at risk for or seeking pregnancy will constitute the target population for this study.

All enrollment and clinical evaluations will be performed at OHSU in Portland, Oregon. Serum samples will be prepared at OHSU and analyzed at the ONPRC Endocrine Core Laboratory under the direction of [name]. De-identified pharmacokinetic data will be analyzed by our consulting pharmacokinetic specialist, [name].

Sources of Materials

The sources of research material for the clinical portion of this proposal will be new specimens obtained purely for this research protocol. The study investigators and/or research assistants/nurses will perform all study procedures.

Potential Risks

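### Part 2's obese-versus-normal chi-square test is called an accuracy check but cannot show agreement with published values, and 10 to 12 controls cannot ensure that agreement for the follicle outcome

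*Combined protocol and SAP*

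**What the plan says.** All references are to the combined protocol and SAP.

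- **Purpose of the arm.** The Part 2 Rationale includes a small normal-BMI group to verify the PK findings. The sample-size text in Part 2, Data Analysis & Sample Size, repeats the verification purpose. It calls the number a convenience sample and then says it should be adequate to "ensure that our PK/PD results are similar to published values in a normal BMI cohort".
- **Size.** The sample-size text refers to "the targeted 10 total number of subjects (after 12 screening) in the control arm". The Part 2 UPA-EC procedures say "enrollment of the 12 participants for this group is complete".
- **Follicle-outcome (PD) check.** Part 2, Data Analysis & Sample Size: "We will check the accuracy of our findings against a normal BMI control group using standard dosing, ECx1 using chi-square test".
- **PK check.** The PK parameter analysis plans parametric or nonparametric tests of each parameter between normal and obese women on the standard dose. It also plans means with standard deviations, and concentration-time curves by BMI group.
- **Power.** The sample-size text says that this group "would achieve the 80% power to detect 47% difference in follicular rupture given the 73 of women taking UPA ECx1". That figure is for a Z test, two-sided, at alpha 0.025. The same paragraph says that the sponsor knowingly did not size the arm for a 20-point difference.
- **Hypothesis.** The Part 2 Hypothesis states: "The peak drug level of UPA-EC is lower in obese women than in normal BMI women". It adds that this harms the therapeutic effect.

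The documents give no numerical published reference value, no similarity margin, no interval criterion and no analysis that sets the controls against published values.

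**The concern.** Two questions share one arm. The first is whether this study's measurements in normal-BMI women agree with the literature. The second is whether obese women differ from normal-BMI women on the same dose. The chi-square test addresses only the second, but the plan presents it as a check of accuracy.

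This sets the check against the hypothesis. If obese women do respond less, accurate measurement should tend to produce a difference, so a significant result is no sign of inaccuracy. If the result is non-significant, the cause may be a small true difference or a small control arm, and accuracy has not been shown.

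At stake is the between-BMI half of Aim 2, and how far the controls can be said to validate the study's methods. With so few controls, a large obese-normal gap could go undetected, and a control rate far from the published one could still look compatible with it.

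**Working it through.** **Inputs from the documents.** Controls: 10 targeted, 12 enrolled. Obese women on standard-dose UPA: 73. Two-sided alpha for the stated power: 0.025. Stated detectable difference: 47 points at 80% power.

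**Assumptions.** The documents give no baseline rate for the PD outcome, no PK coefficient of variation (CV), no reference value and no margin. Ranges are shown for each.

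**1. The plan's own figure.** For a pooled two-sided Z test, power ≈ Φ[(d − z·SE0)/SE1], where
- SE0 = √(p̄(1−p̄)(1/10 + 1/73)), with p̄ the pooled rate
- SE1 = √(pN(1−pN)/10 + pO(1−pO)/73), for normal (N) and obese (O) women
- z = 2.241

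With pO = 0.20 and pN = 0.67: p̄ = (6.7 + 14.6)/83 = 0.257, SE0 = 0.147 and SE1 = 0.156. Power = Φ[(0.47 − 0.330)/0.156] = 0.815.

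Other obese rates give 0.790 (at 0.25), 0.781 (at 0.40) and 0.813 (at 0.45). Over all baseline rates, power for 47 points runs from 0.77 to 0.97. The stated 80% is therefore reproducible for some unstated rates, and I take no issue with it. It describes detecting a very large difference, not showing similarity.

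**2. Power for a 20-point gap.** This is the difference chosen for Part 2's primary comparison. The formula is the same, with controls 20 points higher:

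| Obese rate | 10 controls | 12 controls |
|---|---|---|
| 10% | 37% | 40% |
| 20% | 24% | 27% |
| 30% | 18% | 20% |
| 50% | 13% | 15% |
| 70% | 10% | 14% |

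Even with a true 20-point gap, non-significance is the likelier result throughout.

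**3. Precision of the control proportion.** Exact (Clopper-Pearson) 95% limits:

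| Controls with delay | 95% interval |
|---|---|
| 5/10 | 19% to 81% |
| 7/10 | 35% to 93% |
| 9/10 | 56% to 100% |
| 8/12 | 35% to 90% |

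**4. Precision of the obese-normal difference.** At assumed rates of 50% (n = 73) and 70%:
- 10 controls: 1.96 × √(0.25/73 + 0.21/10) = 0.306, about ±31 points
- 12 controls: 1.96 × √(0.25/73 + 0.21/12) = 0.284, about ±28 points

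**5. What showing PD similarity would need.** Assume a margin of ±20 points around a fixed published proportion, a 90% interval, no true difference and 80% power. Then n = p(1−p)(1.645 + 1.282)²/0.20², which is 54, 52, 45 and 35 at p = 0.5, 0.6, 0.7 and 0.8. With 10 controls the exact power is 0% at p = 0.5, 0.6 and 0.7, and 27% at 0.8. With 12 it is 0% and 21%.

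**6. PK precision.** The 95% limits of a geometric mean are the estimate divided and multiplied by exp(t·s/√n), with s = √ln(1 + CV²), t = 2.262 for n = 10 and t = 2.201 for n = 12. The last column is the simulated power to show similarity within assumed limits of 0.80 to 1.25 of a fixed reference.

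| Assumed CV | Factor, n = 10 | Factor, n = 12 | Power, n = 10 |
|---|---|---|---|
| 20% | 1.15 | 1.13 | 90% |
| 30% | 1.23 | 1.21 | 45% |
| 40% | 1.32 | 1.28 | 15% |
| 50% | 1.40 | 1.35 | 5% |
| 60% | 1.49 | 1.42 | 1.5% |

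**The case against.** **The limitation is disclosed.** The plan calls the arm a convenience sample, says it is not sized for 20 points and states the 47-point limit. It says the number *should* supply adequate data, not that it will. This stands, and the sample size is not the defect. The sentence nevertheless goes on to claim a property that such a sample cannot have for the follicle outcome.

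**The obese-normal comparison belongs in the plan.** Aim 2 calls for it, and the chi-square is the only named PD test between BMI groups. This stands too. The test should be kept; its label is what is wrong.

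**PK may be adequate.** This stands in part. At a CV of 20%, 10 controls could show similarity within 0.80 to 1.25. A blanket statement that the arm cannot show PK similarity would go too far.

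**Aim 2 does not rest on the chi-square alone.** Correct. The peak-level hypothesis is tested in the PK parameter analysis, where descriptive PK output by BMI group is already planned.

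A reader might also infer that a non-significant chi-square will be reported as verified accuracy, or as no effect of obesity. The documents state no such rule. The text invites that reading but does not commit to it.

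**Conclusion.** The point holds for the inference the plan claims from its control arm. The chi-square is mislabelled: whichever way it falls, it says nothing about agreement with published values, and no method or named reference is given for that comparison.

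For the follicle outcome, 10 to 12 controls cannot show similarity under any of the assumptions tried, except for a 21% to 27% chance at a true rate of 80% and a ±20-point margin. The intervals span more than 50 points at 7/10 and 8/12, and the obese-normal difference carries about ±28 to ±31 points at the assumed rates of 50% and 70%. For PK the verdict is conditional on the CV: feasible near 20%, poor from about 40% upwards.

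The arm is secondary and non-randomised. The primary McNemar comparison of the two UPA doses does not use it. This should be corrected, but it does not threaten the main result.

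**What to change.** 1. **Part 2, Data Analysis & Sample Size.** Stop describing the chi-square as an accuracy check. Keep the comparison of obese and normal-BMI women on the standard dose as an Aim 2 estimate, and report the difference in delay proportions with a 95% confidence interval. In the PK parameter analysis, add geometric mean ratios with 95% intervals to the planned tests. State that non-significance will not be read as no difference.
2. **Comparison with published values.** Name the reference values. Beside them, report the control delay proportion with its exact 95% interval, and the control Cmax and AUC geometric means with 95% intervals, as a descriptive comparison.
3. **Part 2 sample-size text.** Replace the *ensure* wording with a statement that the control results will be compared descriptively with published values.

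The cost is a little more analysis and some rewording. No participants are added, which matters because the arm is closed. The sponsor gives up a similarity claim that the design cannot support.
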